### ***10.4 Feasibility***

The Applied Health Research Centre (AHRC) at SMH in Toronto will manage and oversee this trial. AHRC is the largest academic research organization in Toronto, and a designated Research Centre of the Ontario SPOR Support Unit (OSSU) deemed suitable to provide the enabling infrastructure, scientific knowledge and technical support required to conduct patient-oriented research.

## **10.5 Study Product Supply and Accountability**

All study medications will be stored at room temperature (as per the labelling) in a secure location. This is an open label study thus once a participant is randomized, a research coordinator will document the treatment allocation in the case report form and notify the MRP and study team by email and phone of the patient's study treatment allocation (therapeutic or standard care arm). The MRP will then order the study drug in the patient's medical chart and notify the study team. The research coordinator will then email or fax research pharmacy the order. Research pharmacy will follow their SOP to dispense study drug and study drug will be dispensed via research pharmacy to the treating medical team. Returned and unused study drug will be returned to the pharmacy department where it will be destroyed. Research Pharmacy will maintain drug accountability logs, as per their SOPs.

The study medication should be stored in a secure area according to local regulations. The investigator is responsible for ensuring that it is dispensed only to study participants and only from official study sites by authorized personnel, as dictated by local regulations.

The site investigator is responsible for ensuring that the study medication is stored under the appropriate environmental conditions (temperature, light and humidity).

## **11.0 Study Significance**

We believe that this RCT has the potential to **immediately** impact the clinical care of patients with severe COVID-19, internationally, whether our findings are positive or negative as COVID-19 coagulopathy appears to be a highly prevalent complication of severe COVID-19 and may even precede the respiratory manifestations that characterize it (9,10).

In the midst of the COVID-19 pandemic and secondary healthcare crisis, it is time, now more than ever, for randomized care of agents with sound biological plausibility rather than random, best-guess care (22). Thus, our study of a **well understood therapy** with a **predictable adverse effect profile** will, irrespective of our findings, lead to subsequent patients receiving evidence-based therapies and spared from unnecessary harm. Moreover, we are also well positioned to evaluate for ethnic/racial disparities in coagulation/inflammatory responses and effect of anticoagulation.

LMWH and UFH are both licensed anticoagulants in North America therefore, we anticipate swift approval which means that we could **feasibly** launch this RCT at multiple centers **promptly** which is crucially required given the worrisome mortality associated with severe COVID-19 that is rapidly overwhelming hospitals.

## **12.0 Disclosure and Publication Policy**

### **12.1 Publication of Study Results**

Following completion of the study, the lead Principal Investigators are expected to publish the results of the primary and secondary analyses from this trial, in peer-reviewed scientific journals. A detailed authorship policy will be developed and agreed upon by all investigators to determine how best to fairly acknowledge the contributions of relevant parties.

## ***12.2 Data Sharing for Secondary Research***

Data from this study may be used for secondary research. All of the individual participant data collected during the trial will be made available after de-identification through expert determination. These data will be made available as soon as possible following publication, with no end date, as part of data sharing requirements from journals and funding agencies, and in the spirit of open data access.

## ***12.3 Conflict of interest***

The independence of this study from any actual or perceived influence, such as by the pharmaceutical industry, is critical. Therefore, any actual conflict of interest of persons who have a role in the design, conduct, analysis, publication, or any aspect of this trial will be disclosed and managed. Furthermore, persons who have a perceived conflict of interest will be required to have such conflicts managed in a way that is appropriate to their participation in the design and conduct of this trial.

**Table 5. Study Schedule of Events**

	Screening 1,2,\$	Randomization 1,2,\$ (Day 1)	Day 3 \$	Day 7 \$	Day 14 \$	Day 28 \$
Informed Consent	X					
Inclusion/Exclusion	X					
Lowest oxygen saturation (%) on room air	X					
Maximum supplemental oxygen (FiO 2 ) β	X*	X*	X*	X*	X*	X*
Concomitant Medications (including other COVID-19 trial treatments)	X*	X*	X*	X*	X*	X*
Demographics (age, sex, race/ethnicity φ )	X					
Medical History (including smoking, date of COVID-19 symptom onset)	X*					
Height	X**					
Weight	X**					
Dose and frequency of therapeutic anticoagulation administered (treatment arm)		X*	X*	X*	X*	X*
Dose and frequency of LMWH or UFH at thromboprophylactic doses (standard care arm)		X*	X*	X*	X*	X*
Complete Blood Count		X*	X*	X*	X*	X*
Ferritin		X*	X*	X*	X*	X*
D-Dimer	X*	X*	X***	X*	X*	X*
PT		X*	X*	X*	X*	X*
aPTT 		X*	X*	X*	X*	X*
Anti-Xa for UFH 		X*	X*	X*	X*	X*
Anti-Xa for LMWH		X*	X*	X*	X*	X*
INR		X*	X*	X*	X*	X*

Fibrinogen		X*	X*	X*	X*	X*
Lactate dehydrogenase		X*	X*	X*	X*	X*
Troponin		X*	X*	X*	X*	X*
C-Reactive Protein		X*	X*	X*	X*	X*
Creatinine		X*	X*	X*	X*	X*
ALT		X*	X*	X*	X*	X*
Heparin-Platelet Factor 4 Immunoassay		X*	X*	X*	X*	X*
Blood group		X ∞				
Primary outcome assessment 		X*	X*	X*	X*	X*
Length of Hospital Stay		X*	X*	X*	X*	X*
Bleeding Event 		X*	X*	X*	X*	X*
Red Blood Cell transfusion 6a and/or transfusion of any hemostatic blood product/component 6b		X*	X*	X*	X*	X*
Renal replacement therapy 		X*	X*	X*	X*	X*
Organ support (see Appendix 4)		X*	X*	X*	X*	X*
Venous or arterial thromboembolism 		X*	X*	X*	X*	X*
AE/ SAE Assessment 		X*	X*	X*	X*	X*
Optional Biobanking		X†	X†	X†	X†	

\* collected through standard of care when available in the chart;

\*\* height and weight to be collected from the patient's chart or obtained verbally from the patient;

\*\*\* D-dimer will be drawn once on day 2 after randomization (+/- 24 hours); if collected through standard of care, study specific D-Dimer is not needed);

See Appendix 3 for FiO2 for nasal cannula and Venturi mask;

Race/ethnicity of participant collected given known ethnic variation of D-dimers (categories defined in Appendix 1 (23); to obtain verbally from the patient);

∞to be obtained from hospital medical record or verbally from patient if not available from medical record and patient is aware of their blood group;

†Phlebotomy and sample processing on day 1, 3, and 14 OR the time of discharge OR reaching a component of primary outcome OR study withdrawal for any reason;

§Research staff will enter data into REDCap on screening, randomization (day 1), Days 3, 7, 14, and 28 including data from the days in between. Data entered will cover the entire 28 day period. Day 3 will cover Day 2 to Day 3, Day 7 will cover Day 4 to Day 7, Day 14 will cover Day 8 to Day 14, and Day 28 will cover Day 15 to Day 28. If multiple laboratory results are available, the most pathological value since last assessment will be recorded;

within 5 days (i.e. 120 hours) of hospital admission;

screening and randomization can be done on the same day;

 For participants treated with UFH: aPTT or UFH anti-Xa will be drawn according to local institutional UFH nomogram protocol guidance;

If patient is discharged alive before 28 days, vital status will be determined using telephone follow-up by a research coordinator; the use of BIPAP or CPAP at night or when sleeping for sleep apnea is not considered non-invasive mechanical ventilation or organ support for the purpose of this trial; If a patient was discharged alive on mechanical ventilation (invasive or non-invasive) prior to day 28, a call to the patient or a doctor/nurse from the rehabilitation health facility is needed to confirm ventilation status on day 28 and their last day of mechanical ventilation.

Bleeding defined as by ISTH Scientific and Standardization Committee (ISTH-SSC) recommendation: 1) Fatal bleeding, and/or 2) symptomatic bleeding in critical area or organ (such as intracranial, intraspinal, intraocular, retroperitoneal, intraarticular or pericardial, or intramuscular with compartment syndrome, and/or 3) bleeding causing a fall of hemoglobin level of 20g/L or more, or leading to transfusion of two or more units of whole blood or red cells;

6aDefined as  $\geq 1$  unit;

6bDefined as platelet, frozen plasma, prothrombin complex concentrate, cryoprecipitate, fibrinogen concentrate;

defined as continuous renal replacement therapy or intermittent hemodialysis;

defined via diagnostic imaging and/or electrocardiogram where appropriate and possible; AE/SAE will be recorded on any day.

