### 6.1 Bloodwork

No study specific bloodwork will be ordered aside from a single D-dimer test (if not collected through standard of care) up to and including day 3 after randomization for all participants in both study arms. In those on the active treatment arm who are receiving UFH, the aPTT or UFH anti-Xa will be drawn according to local institutional UFH nomogram protocol guidance. Where possible, any study specific blood work will be timed along with regularly scheduled clinical blood work to minimize exposure and use of personal protective equipment. All laboratory results (see Table 5 for Schedule of Events) will be collected from standard of care from admission to hospital discharge, death or 28 days, where available. Laboratory parameters of interest include complete blood count (CBC), PT, aPTT or anti-Xa for UFH (according to local institutional protocol), anti-Xa for LMWH, fibrinogen, blood group, ferritin, lactate dehydrogenase (LDH), troponin, C-reactive protein (CRP), creatinine, alanine aminotransferase [ALT], heparin-platelet factor 4 immunoassay.

Details regarding institutional-specific D-dimer coagulation instrumentation and assay, as well as local reference intervals, including units of measure, will be collected from each site.

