2.2.1 Secondary Outcomes

- 1) Proportion of all-cause death within the first 28 days post-randomization.
- 2) Proportion of subjects with the composite outcome of ICU admission or all-cause death within the first 28 days post-randomization.
- 3) Proportion of subjects with the composite outcome of invasive or non-invasive mechanical ventilation or all-cause death within the first 28 days post-randomization.

- 4) Proportion of subjects with major bleeding, as defined by the ISTH Scientific and Standardization Committee (ISTH-SSC), within the first 28 days post-randomization.
- 5) Proportion of subjects with red blood cell transfusion ≥ 1 unit within the first 28 days post-randomization.
- 6) Proportion of subjects who experienced the following: transfusion of platelets, frozen plasma, prothrombin complex concentrate, cryoprecipitate and/or fibrinogen concentrate within the first 28 days post-randomization.
- 7) Proportion of subjects who had renal replacement therapy defined as continuous renal replacement therapy (CRRT) or intermittent hemodialysis (IHD) within the first 28 days post-randomization.
- 8) Hospital-free days alive up to day 28 post-randomization.
- 9) ICU-free days alive up to day 28 post-randomization.
- 10) Ventilator-free days alive up to day 28 post-randomization.
- 11) Organ support-free days alive up to day 28 post-randomization.
- 12) Proportion of subjects who had venous thromboembolism defined as symptomatic or incidental, suspected or confirmed via diagnostic imaging and/or electrocardiogram where appropriate, recognizing that access to diagnostic imaging may be limited in the midst of the COVID-19 pandemic. Confirmatory testing at a later date once exposure risk/personal protective utilization is not an issue is encouraged within the first 28 days post-randomization.
- 13) Proportion of subjects who had arterial thromboembolism defined as suspected or confirmed via diagnostic imaging and/or electrocardiogram where appropriate, recognizing that access to diagnostic imaging may be limited in the midst of the COVID-19 pandemic. Confirmatory testing at a later date once exposure risk/personal protective utilization is not an issue is encouraged within the first 28 days post-randomization.
- 14) Proportion of subjects with heparin induced thrombocytopenia within the first 28 days post-randomization.
- 15) D-dimer, a COVID-19 disease-related biomarker at day 2 $+$ /- 24 hours post-randomization.

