4.3 Secondary Outcomes Analysis

For the secondary outcomes outlined in section 2.2.1, a chi-squared test of independence will be used to compare the proportions between groups where appropriate. Odds ratios with 95% confidence intervals, and p values will be reported.

Hospital-free days alive, ICU-free days alive, ventilator-free days and organ support-free days will be respectively analyzed as: the number of days out of hospital alive; the number of days out of ICU alive; the number of ventilator-free days alive (alive and free of invasive mechanical ventilation); and the number of organ support-free days alive (alive and free of invasive mechanical ventilation, non-invasive mechanical ventilation, high flow nasal cannula oxygen and vasopressor therapy) through day 28;

death up to 28 days will be assigned a value of -1. These outcomes will be analyzed using ordinal logistic regression.

The post-treatment D-dimer will be compared by means of linear regression (ANCOVA), adjusted for baseline. Since the D-dimer assay differed across sites, the raw values are not comparable. Therefore, the D-dimer will be analyzed as the logarithm of D-dimer x upper limit of normal (ULN) by taking the natural logarithm of the ratio of the actual d-dimer value divided by the ULN for the assay used.

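### For patients with repeat tests, the protocol stores the highest D-dimer of Days 2 to 3 for SAP outcome 15; if testing frequency differs by arm, this can create a spurious difference

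*Protocol*

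**What the plan says.** **Recording rule.** The data-entry footnote to Protocol Table 5 assigns days to each entry: "Day 3 will cover Day 2 to Day 3". It then sets the rule for repeated tests: "If multiple laboratory results are available, the most pathological value since last assessment will be recorded". No laboratory test is exempt. For D-dimer, the most pathological value is the highest.

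**Sampling.** Protocol section 6.1 plans "a single D-dimer test (if not collected through standard of care) up to and including day 3 after randomization". The D-dimer footnote to Table 5 also plans one draw, on day 2 with a 24-hour margin, but adds: "if collected through standard of care, study specific D-Dimer is not needed". Neither place limits how many standard-of-care D-dimers a patient may have in the interval.

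**Analysis.** Protocol outcome 15 is the trajectories of disease-related biomarkers. SAP section 2.2.1 narrows it to "D-dimer, a COVID-19 disease-related biomarker at day 2", with a margin of 24 hours either side. SAP section 4.3 adds: "The post-treatment D-dimer will be compared by means of linear regression (ANCOVA), adjusted for baseline". The outcome is the natural logarithm of D-dimer divided by the assay's upper limit of normal. The SAP does not say which value is used when several fall in the window, and it makes no allowance for the number of tests.

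**Status.** Protocol section 7.2 calls the secondary outcomes exploratory, and SAP section 4.6 also treats them so.

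**The concern.** The SAP describes a measurement at a time. The recording rule supplies a maximum over an interval for any patient tested more than once. The expected maximum of several variable measurements increases with their number, so the recorded D-dimer depends partly on how often the patient was tested.

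That matters for the comparison if testing frequency differs between arms. Standard-of-care tests are ordered by clinicians who know the allocation (Protocol section 3.0). A difference in ordering would raise recorded values in the more heavily tested arm even if treatment had no effect on D-dimer. ANCOVA on baseline cannot correct this, because the number of later tests is not a baseline variable. At stake is the one biomarker comparison that the SAP retains.

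**Working it through.** **Inputs from the documents.** Entry interval Day 2 to Day 3 and the worst-value rule (Protocol Table 5); ANCOVA on ln(D-dimer/ULN) (SAP section 4.3); 231 patients per group (Protocol section 7.1). The plan gives no figure for D-dimer, so its sample size is used only for the number per arm. That figure reproduces: 50% versus 35%, 90% power and two-sided alpha 0.05 give 227 per arm (454 in all) with pooled variance, and 229 per arm (458) at alpha 0.048, against the stated 231 (462).

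**Assumed inputs, not in the documents.** Within-patient SD of ln D-dimer, s = 0.2 to 0.5; residual SD of the ANCOVA, 0.6 to 1.0; the share of patients in each arm with a second test. Repeat values are taken as normal around the patient's own level.

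**Step 1: rise in one patient's recorded value.** The expected maximum exceeds a single draw by 0.564 × s for two draws and 0.846 × s for three.
- Two draws: 0.564 × 0.2 = 0.113 and 0.564 × 0.5 = 0.282 log units, that is +12% to +33%.
- Three draws: 0.846 × 0.2 = 0.169 and 0.846 × 0.5 = 0.423, that is +18% to +53%.

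These are shifts within a patient, not differences between arms.

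**Step 2: difference between arms.** Bias = (difference in share with a second test) × 0.564 × s. With shares of 30% and 10% and s = 0.4: 0.20 × 0.564 × 0.4 = 0.045 log units. The ratio is exp(0.045) = 1.046, about 5%.

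**Step 3: size against the noise.** The standard error is residual SD × √(2/231), which is 0.056 at 0.6 and 0.093 at 1.0. The bias of 0.045 is therefore about 0.5 to 0.8 standard errors. A two-sided 5% test with no treatment effect would reject in 7.7% to 12.8% of trials.

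**Step 4: over the assumed ranges of s and residual SD.**

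| Difference in share with a second test | Spurious ratio | Rejection with no treatment effect |
|---|---|---|
| 0 points | 1.00 | 5.0% |
| 10 points | 1.01 to 1.03 | 5.2% to 8.0% |
| 20 points | 1.02 to 1.06 | 5.7% to 17.3% |
| 40 points | 1.05 to 1.12 | 7.7% to 52.4% |

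**Step 5: check by simulating the ANCOVA** (3,000 runs per setting, 231 per arm). With a second test in 60% versus 40% and s = 0.3, the bias was 0.035 log units after baseline adjustment (formula: 0.20 × 0.564 × 0.3 = 0.034) and rejection was 8.8%. With equal shares, or one value per patient, the bias was about 0.00 and rejection 4.7% to 5.8%.

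**The case against.** The strongest reply is that a one-draw instruction written for D-dimer should govern over a general laboratory rule. With one result per patient, the rule does nothing. But the same footnote lets standard-of-care results stand in for the study draw, and neither document says that D-dimer is exempt. The reply shows that the problem may be rare, not that it is excluded.

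The rest of the case against sets real limits, and rules out stronger readings that a reader might infer.

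- **That testing is known to differ by arm.** Protocol section 6.1 does describe monitoring specific to the experimental arm: "In those on the active treatment arm who are receiving UFH, the aPTT or UFH anti-Xa will be drawn". Those are aPTT or anti-Xa tests, not D-dimer, and UFH is only one of the treatment options. Nothing in the documents shows that D-dimer ordering differs, or in which direction.
- **That sicker patients being tested more is enough to bias the comparison.** Randomization balances baseline severity in expectation. If one arm becomes sicker by Day 3, that is a treatment effect or chance.
- **That the stored value lies outside the SAP's time frame.** Figure 1 counts the day of randomization as day 1, so the Day 2 to Day 3 entry lies broadly within day 2 +/- 24 hours. The defect is that the result decides which eligible value is kept.
- **That the baseline value has the same defect.** A rule applied to values taken before randomization cannot favour an arm.

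The eCRF (version 1.3, cited in SAP section 1) was not available. A separate dated field for this D-dimer would largely resolve the matter, but neither document mentions one.

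**Conclusion.** The point holds as a minor one. Followed as written, the plan analyses a maximum chosen by its result for every patient with repeat D-dimers in the interval, where the SAP describes a value at a stated time. That mismatch needs no assumption about the arms.

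The spurious arm difference is conditional. It requires D-dimer testing to differ in frequency between arms, which the documents do not show. With equal testing, recorded levels rise in both arms and no spurious difference arises. In the worked example the bias is about 0.045 log units (about 5%). This rests on the assumed within-patient SD of 0.4 and the assumed 30% versus 10% with a second test. Larger values in the table need larger imbalances or more within-patient variation. The primary outcome, the sample size and the interim rules are unaffected.

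**What to change.** 1. In the eCRF instruction and the SAP, exempt the outcome 15 D-dimer from the worst-value rule. The rule can stay for the other laboratory tests.
2. In SAP section 4.3, define one dated value per patient: the result closest to a single target time within the SAP window, whatever its level.
3. Reconcile the timing wording first. Figure 1 counts randomization as day 1, which puts day 2 at about 24 hours. The D-dimer footnote to Table 5 speaks of day 2 after randomization but sits in the Day 3 column. Section 6.1 allows up to and including day 3, the data-entry footnote uses Day 2 to Day 3, and SAP section 2.2.1 uses day 2 +/- 24 hours. Section 6.2 equates Day 3 with 48 hours, so a 48-hour target should not be taken for granted.
4. Report the number of D-dimer tests in the window by arm, so that readers can see whether testing differed.

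The cost is one eCRF instruction, a sentence or two in the SAP and one descriptive table. SAP section 4.2 reports that two interim analyses were already conducted, so many entries will exist. Where a patient had several results and only the highest was stored, limited chart re-abstraction is needed. If the eCRF already holds dated individual values, none is needed.

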## Appendix 1. Racial and Ethnic Categories and Definitions

### Definitions for Racial and Ethnic Categories

(based on NIH categories that were modified to be inclusive of additional categories defined at <http://torontohealthequity.ca/wp-content/uploads/2017/05/TC-LHIN-Hospitals-Demographic-Questions-English-visible-v2-1.pdf>)

- **American Indian, Alaska Native, First Nations, Indigenous/Aboriginal, Metis.** A person having origins in any of the original peoples of North and South America (including Central America), and who maintains tribal affiliation or community attachment.
- **Asian.** A person having origins in any of the original peoples of the Far East, Southeast Asia, or the Indian subcontinent including, for example, Cambodia, China, India, Japan, Korea, Malaysia, Pakistan, the Philippine Islands, Thailand, and Vietnam.
- **Black or African American.** A person having origins in any of the black racial groups of Africa. Terms such as "Haitian" or "Negro" can be used in addition to "Black or African American."
- **Hispanic or Latino.** A person of Cuban, Mexican, Puerto Rican, South or Central American, or other Spanish culture or origin, regardless of race. The term, "Spanish origin," can be used in addition to "Hispanic or Latino."
- **Native Hawaiian or Other Pacific Islander.** A person having origins in any of the original peoples of Hawaii, Guam, Samoa, or other Pacific Islands.
- **White.** A person having origins in any of the original peoples of Europe, the Middle East, or North Africa.

The categories and definitions provide a common language to promote uniformity and comparability of data on race and ethnicity. Moreover, federal agencies have a continuing commitment to monitor the operation of its review and award processes to detect, and deal appropriately with, any instances of real or apparent inequities. All analyses conducted on race and ethnicity report aggregate statistical findings and do not identify individuals.

